11.9 Financial Disclosure

Investigators are required to provide financial disclosure information to the Sponsor to permit the Sponsor to fulfill its obligations under 21 CFR Part 54. In addition, Investigators must commit to promptly updating this information if any relevant changes occur during the study and for a period of 1 year after the completion of the study. Details of the financial aspects of the study are addressed in the Clinical Study Agreement.

11.10 Insurance and Indemnity

In accordance with the relevant national regulations, the Sponsor has taken out patient liability insurance for all patients who have given their consent to the clinical study. This cover is designed for the event that a fatality, physical injury, or damage to health occurs during the clinical study's execution.

11.11 Legal Aspects

The clinical study is submitted to the relevant national competent authorities in all participating countries to achieve a clinical trial authorization (CTA).

The study will commence (ie, initiation of study centers) when the CTA and favorable Ethics opinion have been received.

11.12 Conflict of Interest Policy

The independence of this study from any actual or perceived influence, such as by the pharmaceutical industry, is critical. Therefore, any actual conflict of interest of persons who have a role in the design, conduct, analysis, publication, or any aspect of this study will be disclosed and managed. Furthermore, persons who have a perceived conflict of interest will be required to have such conflicts managed in a way that is appropriate to their participation in the study.

12 STUDY ADMINISTRATIVE INFORMATION

[figure not shown]
12.1 Protocol Amendments

Any amendments to the study protocol will be communicated to the Investigators by Medpace or the Sponsor. All protocol amendments will undergo the same review and approval process as the original protocol. A protocol amendment may be implemented after it has been approved by the IRB/IEC unless immediate implementation of the change is necessary for patient safety. In this case, the situation must be documented and reported to the IRB/IEC within 5 working days.

APPENDIX B: CLINICAL LABORATORY ANALYTES

Standard Safety Chemistry Panel

Alanine aminotransferase Albumin
Alkaline phosphatase Amylase
Aspartate aminotransferase Bicarbonate

Blood urea nitrogen/urea C-reactive protein

Calcium Chloride
Creatine kinase Creatinine

Estimated glomerular filtration rate Gamma-glutamyl transferase

Glucose Lactate dehydrogenase

Lipase Phosphate
Potassium Sodium
Total bilirubin Total protein

Uric acid

Hematology

Absolute neutrophil count Hematocrit Hemoglobin Platelets

Red blood cell count and differential [1]

1. Including neutrophils, eosinophils, basophils, lymphocytes, and monocytes. Manual microscopic review is performed

1. Including neutrophils, eosinophils, basophils, lymphocytes, and monocytes. Manual microscopic review is performed only if white blood cell count and/or differential values are out of reference range.

Coagulation

Activated partial thromboplastin time International normalized ratio [1]

Prothrombin time

1. In case there are no normal ranges available for the prothrombin time, the international normalized ratio may be used instead of prothrombin time.

Urinalysis

Bilirubin Blood [1]
Creatinine Glucose

Ketones Leukocyte esterase

Microscopy [2] Nitrite
pH Protein

Specific gravity Urobilinogen

. Including hemoglobin and erythrocytes.

2. Microscopy is performed only as needed based on positive dipstick test results.

Pregnancy Test [1]

Serum human chorionic gonadotropin

Urine human chorionic gonadotropin

1. For female patients of childbearing potential only.

Confidential & Proprietary Version 4.0, 23 November 2022 Page 95 of 102

Endocrinology

Follicle-stimulating hormone [1] Free thyroxine

Thyroid-stimulating hormone Triiodothyronine [2]

- Follicle-stimulating hormone will only be performed in female patients who have spontaneous amenorrhea for at least 2 years to verify their post-menopausal status. Or free triiodothyronine.

Serology

Human immunodeficiency virus

APPENDIX C: EASTERN COOPERATIVE ONCOLOGY GROUP PERFORMANCE STATUS SCORING

Grade	ECOG
0	Fully active, able to carry on all pre-disease performance without restriction
1	Restricted in physically strenuous activity but ambulatory and able to carry out work of a light or sedentary nature, eg, light housework, office work
2	Ambulatory and capable of all self-care but unable to carry out any work activities. Up and about more than 50% of waking hours
3	Capable of only limited self-care, confined to bed or chair more than 50% of waking hours
4	Completely disabled. Cannot carry on any self-care. Totally confined to bed or chair
5	Dead
ECOG =	Eastern Cooperative Oncology Group.

APPENDIX D: DESCRIPTION OF THE IRECIST PROCESS FOR ASSESSMENT OF DISEASE PROGRESSION

Immune-Response Evaluation Criteria in Solid Tumors (iRECIST) is based on the Response Evaluation Criteria in Solid Tumors (RECIST) version (v)1.1 but adapted to account for the unique tumor response seen with immunotherapeutic drugs. iRECIST will be used by the Investigator to assess tumor response and progression and to guide decisions about changes in management.

Assessment at Screening and Prior to the RECIST v1.1 Progression

Until radiographic disease progression based on modified RECIST v1.1, there is no distinct iRECIST assessment.

Assessment and Decision at the RECIST v1.1 Progression

For patients who show radiological progressive disease (PD) by RECIST v1.1, the Investigator will decide whether to continue a patient on study treatment until repeat scans are obtained.

Tumor flare may manifest as any factor causing radiographic progression per RECIST v1.1, including:

• Increase in the sum of diameters of target lesion(s) identified at baseline to ≥20% and ≥5 mm from nadir;

Note: The iRECIST publication uses the terminology "sum of measurements," but "sum of diameters" will be used in this protocol, consistent with the original RECIST v1.1 terminology.

- Unequivocal progression of non-target lesion(s) identified at baseline; and
- Development of new lesion(s).

iRECIST defines new response categories, including unconfirmed PD (iUPD) and confirmed progressive disease (iCPD). For purposes of iRECIST assessment, the first visit showing progression according to RECIST v1.1 will be assigned a visit (overall) response of iUPD, regardless of which factors caused the progression.

At this visit, target and non-target lesions identified at baseline by RECIST v1.1 will be assessed as usual.

New lesions will be classified as measurable or non-measurable, using the same size thresholds and rules as for baseline lesion assessment in RECIST v1.1. From measurable new lesions, up to 5 lesions total (up to 2 per organ), may be selected as New Lesions – Target. The sum of diameters of these lesions will be calculated and kept distinct from the sum of diameters for target lesions at baseline. All other new lesions will be followed qualitatively as New Lesions – Non-target.

Assessment at the Confirmatory Scans

On the confirmatory scans, the patient will be classified as progression confirmed (with an overall response of iCPD), or as showing persistent unconfirmed progression (with an overall response of iUPD), or as showing disease stability or response (stable disease [iSD]/partial response [iPR]/complete response [iCR]).

Confirmation of Progression

Progression is considered confirmed, and the overall response will be iCPD, if ANY of the following occurs:

- Any of the factors that were the basis for the initial iUPD show worsening; or
 - o For target lesions, worsening is a further increase in the sum of diameters of ≥5 mm, compared to any prior iUPD time point;
 - For non-target lesions, worsening is any significant growth in lesions overall, compared to a prior iUPD time point; this does not have to meet the "unequivocal" standard of RECIST v1.1; or
 - o For new lesions, worsening is any of these:
 - An increase in the new lesion sum of diameters by ≥5 mm from a prior iUPD time point;
 - Visible growth of new non-target lesions; or
 - The appearance of additional new lesions.
- Any new factor appears that would have triggered PD by RECIST v1.1.

Persistent iUPD

Progression is considered not confirmed, and the overall response remains iUPD, if:

- None of the progression-confirming factors identified above occurs; AND
- The target lesion sum of diameters (initial target lesions) remains above the initial PD threshold (by RECIST v1.1).

Additional scans for confirmation are to be scheduled 4 weeks to ≤ 8 weeks from the scans on which iUPD is seen. This may correspond to the next visit in the original visit schedule. The assessment of the subsequent confirmation scan will proceed in an identical manner, with possible outcomes of iCPD, iUPD, and iSD/iPR/iCR.

Resolution of iUPD

Progression is considered not confirmed, and the overall response becomes iSD/iPR/iCR, if:

- None of the progression-confirming factors identified above occurs; AND
- The target lesion sum of diameters (initial target lesions) is not above the initial PD threshold.

The response is classified as iSD or iPR (depending on the sum of diameters of the target lesions), or iCR if all lesions resolve.

In this case, the initial iUPD is considered to be pseudoprogression, and the level of suspicion for progression is "reset." This means that the next visit that shows radiographic progression, whenever it occurs, is again classified as iUPD by iRECIST, and the confirmation process is repeated before a response of iCPD can be assigned.

Management Following the Confirmatory Scan

If repeat scans do not confirm PD per iRECIST, as assessed by the Investigator, study intervention is to continue, and the regular scan schedule is to be followed. If PD is confirmed, patients may be discontinued from study intervention.

Note: If a patient has confirmed radiographic progression (iCPD), clinically meaningful study intervention may be continued after consultation with the Sponsor. In this case, if study treatment is continued, tumor imaging should continue to be performed following the intervals as outlined in Section 7.2.

Detection of Progression at Visits After Pseudoprogression Resolves

After resolution of pseudoprogression (ie, after iSD/iPR/iCR), another instance of progression (another iUPD) is indicated by any of the following events:

- Target lesions;
 - Sum of diameters reaches the PD threshold (≥20% and ≥5 mm increase from nadir) either for the first time, or after resolution of previous pseudoprogression. The nadir is always the smallest sum of diameters seen during the entire study, either before or after an instance of pseudoprogression.
- Non-target lesions; or
 - o If non-target lesions have never shown unequivocal progression, their doing so for the first-time results in iUPD; or
 - o If non-target lesions have shown previous unequivocal progression, and this progression has not resolved, iUPD results from any significant further growth of non-target lesions, taken as a whole.
- New lesions;
 - o New lesions appear for the first time;
 - o Additional new lesions appear;
 - o Previously identified new target lesions show an increase of ≥5 mm in the new lesion sum of diameters, from the nadir value of that sum; or
 - o Previously identified non-target lesions show any significant growth.

If any of the events above occur, the overall response for that visit is iUPD, and the iUPD evaluation process (see Assessment at the Confirmatory Scans above) is repeated. Progression must be confirmed before iCPD can occur.

The decision process on the subsequent iUPD is identical to the iUPD confirmation process for the initial PD, with 1 exception, which could occur if new lesions had occurred at a prior instance of iUPD, had not resolved, then worsened (increase in size or number) leading to the second iUPD. If new lesion worsening has not resolved at the confirmatory scan, then iUPD cannot resolve to iSD or iPR. It will remain iUPD until either a decrease in the new lesion burden allows resolution to iSD or iPR, or until new or worsening causes of progression indicates iCPD.

Clinical Study Protocol CYP00
Additional details about the iRECIST are provided in the iRECIST publication. ¹

¹ Seymour L, Bogaerts J, Perrone A, et al. iRECIST: guidelines for response criteria for use in trials testing immunotherapeutics. *Lancet Oncol*. 2017;18(3):e143-e152.

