3.4.1 Definition of Efficacy Endpoints

Disease Control Rate (DCR)

The Disease Control Rate per RECIST 1.1 is defined as the proportion of patients whose best overall response is CR, PR, or SD at ≥16 weeks.

 DCR = 100 x (Number of patients [CR+PR+SD]) / Total number of patients in Full Analysis Set

DCR per iRECIST (iDCR) is defined as the proportion of patients whose best overall response is iCR, iPR, or iSD at ≥16 weeks.

Disease assessments after the start of new anticancer therapy will be excluded from the determination of CR, iCR, PR, iPR, SD, or iSD.

Progression Free Survival (PFS):

PFS per RECIST 1.1 will be defined as the time from the first dose date of study drug to first observation of documented PD per RECIST 1.1 or death due to any cause within 12 weeks of last tumor assessment, per RECIST 1.1:

PFS (months) = (Event/censoring date – first dose date + 1)/30.4375

For patients who have not progressed and are still alive at time of data cutoff for study analysis or who are lost to follow-up, PFS will be right censored. The event or censoring date will be determined based on the conventions listed in **Table 3.1**.

Table 3.1: Progression Free Survival (PFS)

Situation	Date of event or censoring	Outcome
Death before first planned disease assessment	Date of death	Event

Death or disease progression between planned disease assessments	Date of death or first disease assessment showing disease progression, whichever occurs first	Event
No postbaseline disease assessments	Date of first dose	Censored
Initiation of alternate anticancer treatment before disease progression or death (without disease progression beforehand)	Date of last evaluable disease assessment prior to start of alternate anticancer treatment	Censored
Death or disease progression after missing two or more consecutively scheduled disease assessments	Date of last evaluable disease assessment visit without documentation of disease progression before the first missed visit	Censored
Alive and without disease progression	Date of last evaluable disease assessment	Censored

The PFS time will be derived based on scan/assessment dates and not visit dates to determine radiological progression. Assessments/scans contributing towards a particular visit may be performed on different dates. The following rules will be applied for this calculation:

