- Date of radiological progression will be determined based on the earliest assessment/scan dates of the component that triggered the progression (PD using RECIST).
- When censoring a patient for PFS, the patient will be censored at the latest of the assessment/scan dates contributing to a particular overall visit assessment.

PFS per iRECIST (iPFS):

iPFS will be defined as the time from the first dose date of study drug to first observation of documented iCPD per iRECIST or death due to any cause within 12 weeks of last tumor assessment:

• iPFS (months) = (Event/censoring date – first dose date + 1)/30.4375

The iPFS time will be derived based on scan/assessment dates in the same manner as the PFS time derivation. To be counted as disease progression, the iUPD assessment must be confirmed as iCPD at the next iRECIST assessment. In the event that an iUPD response is assessed but the progression is not confirmed (e.g. a later assessment of iSD, iPR, or iCR is observed) then the initial iUPD will not be counted as an event for determination of iPFS. To be conservative, in the case that an assessment of iUPD is recorded and no subsequent evaluable iRECIST assessments are recorded then the iUPD event will be treated as confirmed disease progression.

For patients who have not progressed and are still alive at time of data cutoff for study analysis or who are lost to follow-up, iPFS will be right censored. The same censoring rules for PFS using RECIST 1.1 as specified in **Table 3.1** will be applied.

Overall Survival (OS)

OS is defined as the interval from the start of first study dose to death from any cause. Patients who are alive or lost to follow-up as of the data cutoff date will be censored at the date the patient was last known to be alive:

• OS (months) = (Death date/censoring date – first study dose date + 1)/30.4375

The last date known to be alive for each individual patient may be determined using, but not limited to, the following dates recorded on the eCRF:

- AE start and stop dates,
- Study treatment start and stop dates,
- Laboratory assessment dates,
- Dates of vital signs, physical examination, Eastern Cooperative Oncology Group (ECOG),
- Performance status, and electrocardiogram (ECG) assessments,
- Disease assessment dates,
- Start and stop dates of concomitant medications including procedures and alternative anticancer therapy, and
- Date patient last known to be alive on long-term follow-up.

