On the confirmatory scans, the patient will be classified as progression confirmed (with an overall response of iCPD), or as showing persistent unconfirmed progression (with an overall response of iUPD), or as showing disease stability or response (stable disease [iSD]/partial response [iPR]/complete response [iCR]).

Confirmation of Progression

Progression is considered confirmed, and the overall response will be iCPD, if ANY of the following occurs:

- · Any of the factors that were the basis for the initial iUPD show worsening; or
 - For target lesions, worsening is a further increase in the sum of diameters of ≥5 mm, compared to any prior iUPD time point;
 - For non-target lesions, worsening is any significant growth in lesions overall, compared to a prior iUPD time point; this does not have to meet the "unequivocal" standard of RECIST v1.1; or
 - o For new lesions, worsening is any of these:
 - An increase in the new lesion sum of diameters by ≥5 mm from a prior iUPD time point;
 - Visible growth of new non-target lesions; or
 - The appearance of additional new lesions.
- Any new factor appears that would have triggered PD by RECIST v1.1.

Persistent iUPD

Progression is considered not confirmed, and the overall response remains iUPD, if:

None of the progression-confirming factors identified above occurs; AND

The target lesion sum of diameters (initial target lesions) remains above the initial PD threshold (by RECIST v1.1).

Additional scans for confirmation are to be scheduled 4 weeks to ≤8 weeks from the scans on which iUPD is seen. This may correspond to the next visit in the original visit schedule. The assessment of the subsequent confirmation scan will proceed in an identical manner, with possible outcomes of iCPD, iUPD, and iSD/iPR/iCR.

Resolution of iUPD

Progression is considered not confirmed, and the overall response becomes iSD/iPR/iCR, if:

None of the progression-confirming factors identified above occurs; AND

The target lesion sum of diameters (initial target lesions) is not above the initial PD threshold.

The response is classified as iSD or iPR (depending on the sum of diameters of the target lesions), or iCR if all lesions resolve.

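### After a first iUPD caused only by a new or non-target lesion, Appendix D scores iSD or iPR while that lesion is still present, provided it has not met a worsening criterion

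*Protocol*

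**What the plan says.** Protocol Appendix D lists three possible causes of progression: growth of the baseline target lesions, unequivocal progression of non-target lesions, and new lesions. The first visit with any of them "will be assigned a visit (overall) response of iUPD, regardless of which factors caused the progression".

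At the confirmatory scan, worsening or a new progression factor gives iCPD. If neither occurs, Appendix D has two outcomes. Both begin with the same condition, "None of the progression-confirming factors identified above occurs; AND", and they differ only in the second:

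- Persistent iUPD: "The target lesion sum of diameters (initial target lesions) remains above the initial PD threshold (by RECIST v1.1".
- Resolution: "The target lesion sum of diameters (initial target lesions) is not above the initial PD threshold" (quoted from SAP Appendix C; Protocol Appendix D has the same condition).

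On resolution, "The response is classified as iSD or iPR (depending on the sum of diameters of the target lesions), or iCR if all lesions resolve". The event is then treated as pseudoprogression and the process is reset.

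For a later iUPD, Appendix D declares one exception. It applies to new lesions that were part of an earlier iUPD, had not resolved and then worsened: "If new lesion worsening has not resolved at the confirmatory scan, then iUPD cannot resolve to iSD or iPR".

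SAP 3.4.1 uses these visit responses. "DCR per iRECIST (iDCR) is defined as the proportion of patients whose best overall response is iCR, iPR, or iSD at ≥16 weeks". For iPFS, if an iUPD is followed by iSD, iPR or iCR, "then the initial iUPD will not be counted as an event for determination of iPFS".

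**The concern.** The cause of the iUPD drops out of the decision. When the cause was a new lesion or non-target progression, the test for resolution looks at the target sum, which was not the reason for the iUPD. A metastasis that appeared at week 8 and is still visible at the next scan is then handled like one that has vanished.

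The setting makes this plausible. Protocol 3.1 allows injected lesions to be target lesions, so the target sum can fall through a local effect while disease appears elsewhere. New lesions may themselves be injected (Protocol Table 6 has an exploratory endpoint for them), so a true new metastasis that only stops growing can be labelled pseudoprogression.

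At stake are iRECIST best overall response and iDCR, the protocol's Phase 2a ORR per iRECIST, and in some cases iPFS. For response and disease control the rule can err only in the favourable direction.

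**Working it through.** There is no stated figure to reproduce. The check is to apply the rules as written.

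**1. All outcomes for a first iUPD caused solely by a new or non-target lesion** (target sum below the PD threshold at that visit):

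| Causal lesion at confirmatory scan | Target sum in PR range | Target sum in SD range |
|---|---|---|
| Worse | iCPD | iCPD |
| Present, not worse | iPR | iSD |
| Gone | iPR (iCR if all lesions resolve) | iSD |

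If the target sum crosses the threshold for the first time at this scan, that is a new progression factor and gives iCPD. So no cell is iUPD, and short of iCR the last two rows are identical.

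**2. Illustration A.** The sizes are assumed. The new lesion is at least 10 mm and is followed as a New Lesion – Target. PR is taken as the usual 30% fall, which the appendices do not restate. Baseline target sum is 60 mm.

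| Week | Target sum | New lesion | RECIST v1.1 | As written | Trigger-based rule |
|---|---|---|---|---|---|
| 8 | 40 mm | 12 mm | PD | iUPD | iUPD |
| 16 | 40 mm | 14 mm | – | iPR | iUPD |
| 24 | 40 mm | 16 mm | – | iPR | iUPD |

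- Fall in target sum: (60 − 40)/60 = 33.3%, in the PR range.
- PD threshold from a nadir of 40 mm: 1.2 × 40 = 48 mm (an 8 mm rise, so the 5 mm condition is also met). The sum of 40 mm is not above it.
- New lesion at week 16: 14 − 12 = 2 mm, below the 5 mm worsening criterion. The visit is iPR and the event is reset.
- New lesion at week 24, against its nadir: 16 − 12 = 4 mm, below 5 mm. There is no second iUPD, and the visit is iPR.
- Confirmation: week 24 − week 16 = 8 weeks, and SAP 3.4 asks for at least 6.

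If the new lesion were instead followed as non-target, visible growth would give iCPD. An unchanged lesion gives iPR under either label.

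**3. Do later rules catch it?**
- Best overall response (SAP 3.4) is the best designation up to iCPD, so an earlier iUPD does not cap a later iPR.
- The 6-week confirmation and 16-week iSD rules do not help. After the reset, a persisting lesion counts again only if it grows or further lesions appear.

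**4. iPFS.** Under the trigger-based rule, illustration A never reaches iCPD. It becomes an iPFS event only if follow-up ends on an iUPD, which SAP 3.4.1 treats as confirmed progression.

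A delay is also possible. Illustration B: baseline sum 60 mm, then 58 mm throughout, with a new lesion of 10/14/18/22 mm at weeks 8/16/24/32.
- As written: iUPD; iSD at week 16 (14 − 10 = 4 mm); a second iUPD at week 24 (18 − 10 = 8 mm). iCPD comes at week 32 at the earliest.
- Trigger-based: iUPD, iUPD, then iCPD at week 24 (8 mm above the week 8 iUPD).
- Week 32 as written is open. Against week 24 the growth is 22 − 18 = 4 mm, which does not confirm. Against the already reset week 8 scan it is 22 − 10 = 12 mm, which does.

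**5. Size per patient.** 1/6 = 16.7 percentage points of iDCR in Phase 1b; 1/30 = 3.3 points of ORR per iRECIST in one planned Phase 2a arm.

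**The case against.** Several points on the other side are sound.

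- A reader might infer that resolution rests on the target sum alone. It does not: growth of 5 mm or more in the new-lesion sum, visible growth of new non-target lesions, further new lesions, significant non-target growth or any new progression factor gives iCPD. Only lesions that persist without meeting such a criterion are affected.
- A reader might infer that Appendix D contradicts itself. The rule for a later iUPD is a declared exception, and it covers new lesions that had not resolved and then worsened, which is a different picture. Appendix D also foresees non-target progression that is still unresolved after a reset, so the lenient rule may be deliberate. What stands is that no reason is given for treating the first iUPD more leniently.
- The appendix defers to the iRECIST publication for detail. Whether the rule, or the proposed change, agrees with that source cannot be judged here.
- Reach is limited. The SAP covers Phase 1b only, after termination. It plans descriptive summaries without formal testing and no longer lists ORR per iRECIST. RECIST v1.1 DCR and PFS are reported alongside, so a divergence would be visible.

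These points narrow the concern but do not remove it. The scoring in the table follows from the text, and the SAP still reports iRECIST best overall response, iDCR and iPFS.

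**Conclusion.** The concern holds in this limited form. After a first iUPD caused only by a new lesion or non-target progression, with the target sum below the threshold and no worsening criterion met, both appendices require iSD or iPR and a reset even though the lesion is still there. This favours iRECIST best overall response, iDCR and the protocol's ORR per iRECIST.

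One patient who would not otherwise count moves iDCR by 16.7 points with n = 6. The 3.3 points with n = 30 has no planned analysis in the current SAP. The illustrations rest on assumed lesion sizes.

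Three further inferences are not supported:
- The primary Phase 2a ORR uses RECIST v1.1 and is not affected.
- iPFS is not always lengthened. It changes only where the reset delays iCPD, or where follow-up would otherwise end on an iUPD.
- No rate of misclassification can be given. The documents do not say how often progression starts with new or non-target lesions alone. A count of all such iUPDs that are not worse at the next scan would wrongly include lesions that truly resolved.

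**What to change.** For endpoint derivation, reconcile the Persistent iUPD, Resolution of iUPD and later-iUPD paragraphs in Protocol Appendix D and SAP Appendix C. An iUPD resolves to iSD or iPR only if all three hold:

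1. no progression-confirming factor occurs;
2. the target sum is below the PD threshold (this wording also settles a sum exactly at the threshold);
3. the new-lesion or non-target progression that caused the iUPD has decreased or resolved.

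Otherwise, without a confirming factor, the visit remains iUPD. This carries the principle of the later-iUPD exception over to the first iUPD and to non-target lesions. It is an extension and should be described as one. The rules on continuing treatment are not part of this change.

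The cost is a few sentences in each appendix and one derivation check. Appendix D already has new and non-target lesions followed. The downside is that ORR per iRECIST and iDCR may come out slightly less favourable.
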